Sleep stages, arousals and respiratory events will be scored by a registered polysomnographic technologist blinded to the treatment allocation according to the American Academy of Sleep Medicine recommended criteria.

Muscle activity will be quantified using standard procedures described in our previous studies (1, 23, 24). Briefly, the raw EMG_{GG} signal will be rectified and smoothed with a 100 msec window. The peak phasic, as well as tonic, activity of the smoothed signal will be identified for each breath. Data from quiet wakefulness (free of swallowing and movement artifacts) will be averaged to determine the peak phasic and tonic activities during this state. The same will be done for stable NREM and REM sleep (free of arousals and other artifacts). Pharyngeal muscle responsiveness will be determined by calculating the slope and intercept of the esophageal pressure versus muscle EMG relationship.

Reimbursement

Subjects will receive \$100/night for participation in each overnight study (TOTAL = \$200). Reimbursement for parking expenses will be provided.

If the subjects will repeat a part or the entire protocol because of insufficient data collection, they will be reimbursed \$100 for any extra night.

If the subjects will take part to the additional nights on atomoxetine and oxybutynin alone, they will be paid \$100/night (total \$400).

VI. BIOSTATISTICAL ANALYSIS

Sample size: Based on previous data from the study of the noradrenergic drug desipramine in OSA patients, 20 patients will enable us to detect a reduction in AHI of $50\pm75\%$ (80% power, alpha 0.05), primary outcome. 20 patients will also enable us to detect a $100\pm150\%$ increase in genioglossus activity (80% power, alpha 0.05), secondary outcome. Accounting for a 20-50% failure rate of these kind of physiology studies we anticipate that we may need to enroll up to 30 patients to conclude the study

Variables of interest will be compared using a Wilcoxon matched-pairs signed rank test, with a p-value <0.05 considered statistically significant. To compare the effect of placebo, ato-oxy, atomoxetine alone and oxybutynin alone in the participants who will perform 4 study nights, we will use the Friedman's test with a post-hoc analysis (Wilcoxon) in which each treatment will be compared to placebo; the post-hoc analysis will be conducted with Bonferroni correction (p-threshold=0.017).

VII. RISKS AND DISCOMFORTS

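### Holm's step-down test would recover some single-drug power in the four-night analysis that single-step Bonferroni at 0.017 gives up, under the same nominal 0.05 family-wise bound

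*Combined protocol and SAP*

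**What the plan says.** Section VI (Biostatistical Analysis) sets a general rule for paired comparisons: "Variables of interest will be compared using a Wilcoxon matched-pairs signed rank test, with a p-value <0.05 considered statistically significant". For participants with four study nights it adds: "we will use the Friedman's test with a post-hoc analysis (Wilcoxon) in which each treatment will be compared to placebo". The three contrasts are therefore the combination, atomoxetine alone and oxybutynin alone, each against placebo. On multiplicity it says "the post-hoc analysis will be conducted with Bonferroni correction (p-threshold=0.017"). No step-down procedure is mentioned.

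The sample-size statement in the same section belongs to the main two-night comparison: "20 patients will enable us to detect a reduction in AHI of $50\pm75\%$ (80% power, alpha 0.05), primary outcome". Nothing is said about the number of patients, the effect size or the power for the single-drug contrasts.

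The last paragraph of Section IV (Subject Enrollment) limits the two single-drug nights to patients whose genioglossus activity and OSA severity improved on the combination night. The four-night subset is thus a selected part of the evaluable patients, of whom 20 are planned.

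**The concern.** A fixed 0.017 holds each single-drug contrast to the strictest threshold even after the combination contrast has been rejected. The new information from the two extra nights is what each drug does alone, and it comes from a small subset. Holm's procedure has the same nominal family-wise bound and needs no extra assumption about how the contrasts are correlated. Once the combination contrast, presumably the largest, is rejected, the single-drug contrasts face 0.025 and then 0.05. Staying with Bonferroni gives up some chance of a single-drug finding without gaining a tighter nominal bound.

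**Working it through.** **1. The plan's own figures.**
- Standardized paired effect: 50/75 = 0.667 (the genioglossus figures, 100/150, give the same). For a two-sided paired t-test at 0.05 with n = 20, the noncentrality is 0.667 × √20 = 2.98 and the power is 80.7%. The stated 20 patients at 80% power is reproduced. A simulated exact Wilcoxon test at n = 20 gives 78.8%.
- Threshold: 0.05/3 = 0.0167, printed as 0.017.

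**2. The two rules.** Order the three p-values p(1) ≤ p(2) ≤ p(3).
- Bonferroni: reject every contrast with p ≤ 0.05/3.
- Holm: reject p(j) while p(j) ≤ 0.05/(4 − j), that is 0.0167, 0.025, 0.05, and stop at the first failure.

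Any p-value at or below 0.05/3 passes every Holm step up to its own, so Holm rejects whatever Bonferroni rejects. Both bound the family-wise error at 0.05 under any dependence, provided the p-values are valid.

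**3. Power gain.** Assumptions, none of them given in the documents for this subset:
- 8 to 20 completers;
- normal night values, and differences from placebo with SD 1;
- one shared placebo night, so that contrasts correlate 0.5;
- exact two-sided signed-rank tests;
- no selection of patients.

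There were 40,000 simulated trials per setting. With the combination at 1.2 SD and both single drugs at 0.667 SD, power per single drug was:

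| n | Bonferroni | Holm | Gain (points) |
|---|---|---|---|
| 8 | 17% | 24% | 7 |
| 10 | 23% | 33% | 10 |
| 12 | 34% | 43% | 9 |
| 15 | 44% | 57% | 13 |
| 20 | 61% | 74% | 13 |

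Other settings:
- Combination 1.2 SD, one drug 0.667 SD, the other inert: the active drug gains about 4 points at n = 8, 6 at n = 15 (44% to 50%) and 7 at n = 20.
- Combination 1.2 SD, both single drugs 0.333 SD: about 2 points at n = 8, 4 to 5 at n = 15 and 7 at n = 20.
- Combination only 0.667 SD, one drug 0.667 SD, the other inert: about 2 to 4 points over n = 8 to 20.

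**4. Error actually spent, no selection.** At n = 20, with the combination effective and both single drugs null, the family-wise error is about 0.028 for Bonferroni and 0.042 for Holm. At n = 15 with one drug inert, that drug's false-positive rate rises from 1.5% to 3.5%.

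**5. Effect of selecting improvers.** If all n selected patients improved on AHI, the two-sided exact p for the combination is 2/2^n. That is 2/64 = 0.031 at n = 6 and 2/128 = 0.0156 at n = 7, so from n = 7 this contrast always passes 0.0167 and Holm always relaxes the next threshold. Selection on combination minus placebo also favours patients whose placebo night happened to be bad, and that night enters every single-drug contrast. In an illustrative simulation (n = 20, independent night errors of equal variance, both single drugs null), the single-drug family-wise error was:

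| Combination effect | Bonferroni | Holm |
|---|---|---|
| 1.2 SD | 0.048 | 0.071 |
| 0.667 SD | 0.12 | 0.16 |

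**The case against.** The strongest reply is that nothing here is wrong. The test, the family of contrasts, the correction and the threshold are all specified in advance. Single-step Bonferroni is valid and conservative. The analysis is a conditional add-on, and the main two-night comparison, on which the study is sized, is untouched. All of that stands, and it limits the point to an efficiency suggestion.

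Three stronger readings are tempting, and the documents support none of them.
- *Holm always gains 7 to 13 points.* This range needs both single drugs at 0.667 SD, which is the planning ratio for the main comparison, and an assumed 1.2 SD for the combination. The documents assign neither to the four-night subset.
- *The 0.017 threshold is the main limit on a single-drug finding.* Even with Holm and the favourable effects, power is 24%, 33% and 43% at n = 8, 10 and 12. Subset size limits the analysis more.
- *Holm changes nothing about error control.* Only the nominal bound is the same, and Holm spends more of it.

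The selection argument also has force. In this subset the combination contrast is close to a foregone conclusion, so Holm's relaxation is partly bought by the entry rule. With the placebo night reused, the 0.05 bound need not hold, and Holm moves the error further up. This does not make Bonferroni adequate, since its error also reaches 0.12 in one illustration. It does mean that a change to Holm should not be presented as guaranteeing 0.05.

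**Conclusion.** The point holds as a cheap improvement. The Bonferroni rule is valid but more conservative than it needs to be. Holm keeps the same nominal bound, loses no rejection that Bonferroni at 0.05/3 makes, and adds about 2 to 13 points of power per single drug over 8 to 20 completers. Where in that range the gain falls depends on the single-drug and combination effects and on the number of completers, all of which are assumptions here.

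A reader might infer that the planned analysis is faulty or that the main result is affected. Neither follows. Nor does a nominal 0.05 mean an actual 0.05: both procedures assume valid p-values, and the entry rule in Section IV puts that in doubt. The selection figures are illustrative, since they depend on the assumed night-to-night error and the documents do not define improvement.

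**What to change.** In Section VI, replace the Bonferroni clause with: *post-hoc contrasts against placebo will be tested by exact Wilcoxon signed-rank with Holm's step-down adjustment at two-sided nominal family-wise 0.05, and Holm-adjusted p-values will be reported.* Make the change before unblinding.

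The cost is one clause, with no extra patients, nights or data. There are two downsides. Holm has no equally simple matching simultaneous confidence intervals, although the plan specifies none and Bonferroni intervals could still be shown. Its actual error is also somewhat higher within the 0.05 bound.

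The bias from selecting improvers and reusing their placebo night has to be dealt with separately. Until it is, single-drug p-values under either procedure should be reported with that caveat.
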